6.3 Stratification factors and intervention allocation plan for randomized studies. N/A

6.5 Stratification factors and their impact on design. N/A

6.6 Early stopping rules, if appropriate. N/A

6.7 Definition of and allowance in design for unevaluable/ineligible participants. No unevaluable and/or ineligible participants will be included in this study.

6.8 Analysis Plan.

Aim a) To examine the feasibility and acceptability of a group-based, stress-management and resiliency intervention delivered via videoconferencing technology for lymphoma survivors who are within 2 years of having completed cancer treatment.

Descriptive statistics, including means, frequencies, and ranges will be used to describe the sample and to summarize feasibility, acceptability, and program satisfaction. Feasibility outcomes will be assessed by determining the proportion of individuals who were recruited, screened, and enrolled in the study. Response frequencies will summarize reasons for ineligibility and refusal. We will also determine the proportion of enrolled participants who complete the study. Participants who complete at least 75% of the treatment sessions (6 out of 8 sessions) will be identified as treatment completers. We will examine the proportion of individuals who attend each session as well as the percent who adhered to recommended relaxation practice (defined as RR

elicitation at least 3 days/week, as measured by the RR practice logs (Appendix 8.3). For acceptability, response frequencies will summarize quantitative feedback on the 3RP Acceptability Questionnaire (Appendix 8.5).

Aim b) To explore the feasibility and acceptability of collecting hair samples to examine changes in stress reactivity.

Feasibility metrics for the hair sampling include hair return rates. For measures of acceptability, response frequencies will summarize quantitative feedback from question 13 on the 3RP Acceptability Questionnaire (Appendix 8.5) about the acceptability of hair collection procedures. Together with qualitative feedback from the Exit Interviews (Appendix 8.7), this information will be used to inform the feasibility and acceptability of hair cortisol measurement. Hair cortisol samples will be analyzed by [name] laboratory at the University of Massachusetts, Amherst. Pearson correlation or Spearman's rank correlation will be used to examine the association of hair cortisol with each of our exploratory psychosocial outcomes.

Exploratory Aim c) We will examine the preliminary effects of the intervention on psychosocial measures of fatigue, mindfulness, depressed mood, anxiety, and stress.

Preliminary outcome data may be used to inform future assessment instruments and methods. We may also conduct exploratory hypothesis testing to examine preliminary changes in our proposed intervention targets (changes in fatigue, mindfulness, depressed mood, anxiety, stress). A priori statistical tests of intervention-related changes will be planned for a future efficacy trial of this intervention. We will compare baseline demographic and clinical characteristics between completers and non-completers using chi square tests and t-tests. Paired samples T-tests will be used to examine pre and post-intervention differences (T2 vs T1) at $p < .05$ for each of our exploratory outcomes (e.g. CAMS-R). We will also assess the sustained effects of treatment with a repeated measures ANOVA analysis, including the 3 survey time points. This analysis will allow us to assess if there is a trend towards maintenance of treatment effects but is not powered to detect significant differences.

Exit interviews (Appendix 8.7) will be audio-recorded and transcribed; NVIVO software will be utilized in the thematic analysis, which will be led by [name] and the study RA under the mentorship of [name], who directs the Qualitative Research Core at MGH. [name] and the study RA will meet on a weekly basis to discuss the coding framework, categories, and coding plan. To ensure coding reliability, coding discrepancies will be resolved through discussion and comparison of raw data. Coding will continue until a high level of reliability ($\text{Kappa} = > 0.80$) is established.

6.9 Handing of missing data in the analysis.

This phase of the study is intended to test the feasibility and acceptability of the stress management program. We will explore differences between study completers and non-completers on patient demographic and other relevant variables to inform the next phase of this trial. We will assess whether the mechanism of missing data is missing at random. We will perform sensitivity analysis using: 1) a completer analysis limited to those who have complete data and 2) multiple imputations for missing data.⁶⁰ To address missing data at follow-up, participants who are no longer interested in participating in the 3RP sessions will still be given the option to complete follow-up assessments.

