Preliminary studies: BHI investigators have demonstrated the efficacy of the 3RP in decreasing stress and improving psychological and physical health symptoms among patients with chronic pain,¹⁸ insomnia,¹⁹ infertility,²⁰ and other medical symptoms.²¹ Recently, Drs. [name] and [name] adapted the 3RP and conducted an NCI-funded pilot with 28 cancer interpreters.²² Post-treatment follow-up results indicated improvements in job satisfaction ($p=0.02$; Cohen's $d=.41$) and stress reactivity (MOCS-A; $p=0.13$; Cohen's $d=.33$). [name] has also led a 3RP group treatment for a randomized trial (PI: [name]., Ph.D., DF/HCC 13-266) examining the efficacy of this treatment among patients diagnosed with the precursors of multiple myeloma. Currently, the feasibility of delivering a group 3RP virtually via Partners Health Care Telehealth videoconferencing software is being tested with parents of children with special needs (PI: [name], funded by the Dan Marino Foundation, Partners IRB Protocol #: 2016P001622).

Using information gained from qualitative interviews with lymphoma survivors conducted during Phase 1 of this trial (DF/HCC 16-396), we adapted the 3RP to target the needs of lymphoma survivors transitioning off treatment. In addition, Phase 1 interview participants endorsed hair cortisol as an acceptable method of cortisol sampling and expressed that they would be interested in providing hair samples to learn more about their change in stress levels. As such, we have included hair cortisol measurement as an optional portion of this Phase 2 study.

Significance and Innovation: The proposed program is unique in many ways: 1) It targets a group of survivors who are at high risk for negative psychosocial outcomes and for whom there is a paucity of targeted treatments; 2) It tests a unique, evidence-based treatment that is patient-centered in its development and delivery; 3) It offers a treatment modality (i.e., mind-body approach) that is widely accepted and used by survivors;^{23,24} and 4) It offers a virtual delivery platform that may appeal to a population whose symptoms (e.g., chronic fatigue) may pose an obstacle to accessing support services.

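### The three-survey ANOVA named for sustained effects (exploratory Aim c) does not by itself distinguish kept from lost change, and section 6.9 promises a missing-at-random check that observed data cannot provide

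*Combined protocol and SAP*

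**What the plan says.** Section 6.8, Exploratory Aim c, gives two analyses of change for the psychosocial scales.

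- Short-term change: "Paired samples T-tests will be used to examine pre and post-intervention differences (T2 vs T1"), each at the 5% level.
- Lasting change: "We will also assess the sustained effects of treatment with a repeated measures ANOVA analysis, including the 3 survey time points". The plan adds that this will show whether there is "a trend towards maintenance of treatment effects but is not powered to detect significant differences".

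No comparison of follow-up with baseline or with the post-programme survey is named, and sustained is not defined. The plan limits its ambitions: hypothesis testing is introduced as something the team may do, formal tests are left to a future efficacy trial, and "Preliminary outcome data may be used to inform future assessment instruments and methods".

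On missing data, section 6.9 says "We will assess whether the mechanism of missing data is missing at random". It lists two sensitivity analyses: "1) a completer analysis limited to those who have complete data and 2) multiple imputations for missing data". It also says "We will explore differences between study completers and non-completers on patient demographic and other relevant variables". No main missing-data approach is stated.

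**The concern.** The question is whether change seen at the end of the programme is still there at the follow-up survey, four to six weeks after the last session (section 5.5.1). The T2 vs T1 test uses no follow-up data. The ANOVA time test uses all three surveys, but it answers a different question: whether the three means are all equal. Means of (0, d, d) and (0, d, 0) both violate equality. A significant result could therefore be reported as a trend towards maintenance when the change has gone.

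The missing-data wording raises two further problems. A conventional repeated measures ANOVA drops anyone who misses a survey, and the plan does not say whether that or an imputed analysis is the main result. A check that appears to confirm missing at random would also give false reassurance. Observed data can count against missing completely at random, but they cannot separate missing at random from missing not at random.

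**Working it through.** **The plan's own figure.** The only power figure (section 6.2) is 90% for mean session participation 5.5 points above 75%, with n=30, SD 10 and one-sided 5%. A one-sample t calculation with standardised difference 0.55 gives 0.903, so it reproduces. It concerns feasibility; there is no figure for Aim c to reproduce.

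**Inputs.** n=40 is the number section 5.1 expects to take part in the programme. d=0.33 is the MOCS-A effect from the earlier pilot in 28 interpreters (section 1.2), read here as SDs of the raw score. The between-survey correlation ρ is not in the documents; I assume 0.6 and show 0.37 to 0.7. The lower end is what the pilot implies if p=0.13 is a two-sided paired t-test on all 28: t=1.56, so d in SDs of change is 1.56/√28 = 0.295, and ρ = 1 − (0.33/0.295)²/2 = 0.37.

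**Step 1: the ANOVA time test.** Under equal correlations, λ = n·Σ(μ−μ̄)²/(1−ρ), with 2 and 2(n−1) degrees of freedom. The sum is (2/3)d² for both (0, d, d) and (0, d, 0), so power is identical whatever n, d and ρ are. At n=40, d=0.33, ρ=0.6: λ = 40 × (2/3) × 0.1089/0.4 = 7.26.

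**Step 2: the T3-T1 contrast.** The standard error is √(2(1−ρ)/n) = √(0.8/40) = 0.141 SD, and the 95% confidence interval is ±0.286 SD.

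| n, d, ρ | ANOVA, kept or lost | T3-T1, kept | T3-T1, lost |
|---|---|---|---|
| 40, 0.33, 0.37 | 45% | 44% | 5% |
| 40, 0.33, 0.6 | 65% | 62% | 5% |
| 40, 0.33, 0.7 | 79% | 75% | 5% |
| 30, 0.33, 0.6 | 52% | 50% | 5% |
| 40, 0.5, 0.6 | 96% | 93% | 5% |

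The T3-T1 interval runs from ±0.36 SD (ρ=0.37) to ±0.25 SD (ρ=0.7) at n=40. If 0.33 is instead in SDs of change, T3-T1 power at n=40 is 53%.

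**Step 3: both named tests together.** In simulation (n=40, d=0.5, ρ=0.5), the ANOVA and T2 vs T1 are both significant in 84.3% of runs if change is kept and 84.2% if lost.

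**Step 4: unequal correlations.** With first-order autoregressive correlation of 0.6 (n=40, d=0.5), the ANOVA rejects in 90.0% of runs if kept and 95.5% if lost. Exact equality goes, but the test is still not specific to maintenance.

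**Step 5: trend read as a linear contrast.** With equally spaced scores (−1, 0, 1) the contrast is exactly T3-T1, and lost change contributes nothing. Scored by survey week, the midpoints of the section 5.5.1 windows are weeks −2, 8 and 12, centred to −8, 2 and 6. Kept change gives 2d + 6d = 8d and lost change 2d, a ratio of 25% (9% to 38% over the corners of the windows). At n=40, d=0.33, ρ=0.6, the week-scored contrast is significant 71% of the time if kept and 10% if lost.

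**Step 6: T3-T2 alone.** If a 0.33 SD change is fully lost (n=40, ρ=0.6), T3-T2 is still non-significant 38% of the time.

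**Step 7: missing surveys.** If each later survey is returned by 80% independently (assumed), complete cases are 40 × 0.8² = 25.6; the SE of T3-T1 is 0.18 SD, against 0.16 SD using all available surveys. If return of T3 depends on the T2-T1 change (assumed logit slope 1), complete cases give 0.41 for a true 0.33 and 0.08 for a true 0. Regression imputation of T3 from T1 and T2 gives 0.33 and 0.00 under the same model.

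**Step 8: what cannot be checked.** If 20% are missing (assumed) and their unseen T3 scores lie 0.5 SD from what would be imputed, the T3 mean moves by 0.2 × 0.5 = 0.10 SD with no change in the observed data. Over 10-30% missing and shifts of 0.25-1 SD, the range is 0.025-0.30 SD.

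**The case against.** Four points deserve weight.

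First, a reader might infer that repeated measures ANOVA cannot address maintenance at all. That goes too far. The three means come with the analysis, and their direction separates kept from lost change. An equally spaced linear trend is T3-T1 itself, and even the week-scored version separates the two cases fairly well. What stands is that the plan names neither contrast nor reading, and the default time test does not answer the question. It is also fair to say that T2 vs T1 is never offered as evidence of maintenance.

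Second, a reader might infer that dropout linked to early change would bias the results uncorrected. The documents do not support this. Section 6.9 already plans multiple imputation, which removes the bias in step 7 if the imputation model includes the earlier surveys. The bias figures also depend on an assumed dropout model. What stands is that both approaches are labelled sensitivity analyses, so it is unclear which is the main one.

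Third, the plan admits the analysis is unpowered. That is a separate matter: a larger sample would make the time test reject more often for kept and lost change alike.

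Fourth, the missing-at-random point is largely one of wording, since the useful observed-data comparison of completers with non-completers is already planned. I agree, but the sentence still promises something that cannot be delivered.

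**Conclusion.** The concern holds as a gap in specification. A significant three-survey ANOVA does not show that change lasts to follow-up, and the plan does not name the contrast that would. The equality of power for kept and lost change is exact under equal correlations and does not depend on the assumed n, d or ρ; the percentages do. The missing-at-random statement cannot be fulfilled as written, and the main missing-data analysis is unstated.

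The stakes are low. Aim c is exploratory, its testing is optional and stated to be unpowered, and no primary feasibility or acceptability endpoint depends on it. Nor should a reader take a properly chosen contrast as evidence that the programme's benefit persists: with a single arm it shows only that change from baseline persists.

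**What to change.** In section 6.8, for each exploratory scale, report mean changes T2-T1, T3-T1 and T3-T2 with 95% confidence intervals. Judge maintenance from T3-T1 together with T3-T2, and state that a non-significant T3-T2 alone is not evidence of maintenance. Make the main analysis one that uses all available surveys: either a mixed model with time as a categorical factor or the multiple imputation already planned. Keep the completer analysis as sensitivity. Describe results as persistence of change from baseline. Label the intervals exploratory and unadjusted for multiplicity; with one score for each of the 13 instruments in the section 5.4 schedule there would be 13 × 3 = 39, and more if individual items or domains are analysed.

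In section 6.9, replace the missing-at-random check with a report of observed predictors of missingness, building on the planned completer comparison, and state missing at random as an assumption of the main analysis.

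The cost is a few sentences of wording and a little more analysis work. No new data, visits or participants are needed.
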